## 10.8.1.3. Reporting Requirements for Study Deviations

All study deviations must be reported on the eCRF regardless of whether medically justifiable, an inadvertent occurrence, or taken to protect the subject in an emergency. The date and reason for each deviation will be documented (21 CFR 812.140 Records).

In order to protect the rights and interests, safety and health of subjects, the deviation occurred under emergency situations that cannot be timely reported shall be reported in written form afterwards in accordance with relevant regulations as soon as possible.

The following examples are deviations that could impact subject safety, affect the integrity of study data and/or affect subject's willingness to participate in the study. These deviations are significant and require immediate sponsor notification upon investigator awareness.:

- Failure to obtain informed consent/assent, i.e., there is no documentation of informed consent/assent
- Informed consent/assent obtained after initiation of study procedures
- Continuation of a subject who did not meet all inclusion/exclusion criteria
- Performing study procedure not approved by the IRB
- Failure to inform IRB and sponsor of reportable AEs (see Section 12) per the requirements of the CIP
- Investigational study device dispensed without obtaining informed consent
- Device dispensing error (i.e., use of an investigational device on a non-study subject)
- Study visit conducted outside of required timeframe that, in the opinion of the PI, may affect subject safety

Reporting of all other study deviations should comply with IRB policies and/or local laws and must be reported to Medtronic as soon as possible upon the center becoming aware of the deviation. Reporting of

deviations must comply with IRB policies, local laws, and/or regulatory agency requirements. Refer to Investigator Reports, Table 10, for specific deviation reporting requirements and timeframes for reporting to Medtronic, IRB, and regulatory agency (if applicable).

### **10.8.2. Analyzing Deviations**

Medtronic is responsible for reviewing deviations, assessing their significance, and identifying any additional corrective and/or preventive actions (e.g. amend the CIP, conduct additional training, terminate the investigation). Repetitive or serious investigator compliance issues may result in initiation of a corrective action plan with the investigator and investigational center, and in some cases, necessitate suspending enrollment until the problem is resolved or ultimately terminating the investigator's participation in the study.

## **10.9. Subject Withdrawal or Discontinuation**

Subjects may choose to withdraw from the study at any time by notifying investigational center staff of their intent.

If a subject chooses to end his or her study participation or if a subject is removed from the study at the Investigator's discretion or failure to meet the study requirements, the reason for termination must be documented both in source documents and Exit eCRF. All study devices and supplies must be returned and documented both in source documents and on an eCRF.

Subjects may also be withdrawn from the study at the discretion of the Investigator. A subject may be withdrawn from the study if:

- In the opinion of the Investigator, the subject's health or safety would be compromised by continuing in the study
- In the opinion of the Investigator, it is in the subject's best interest to discontinue participation in the study
- The subject is found to no longer meet all inclusion criteria, or is found to meet one or more exclusion criteria
- The subject fails to comply with one or more study requirements

Subject will be withdrawn from the study if subject experiences diabetic ketoacidosis, unconsciousness or severe hypoglycemia.

Documentation of the reason(s) leading to subject withdrawal will be kept in the subject's source file

## **10.10. Stopping Rules**

### **10.10.1. Subject Stopping Rules**

- Subject is exhibiting signs and symptoms of DKA (see DKA definition in Section 12.1)
- Severe hypoglycemia (see severe hypoglycemia definition Section 12.1)

- YSI™\* glucose greater than (>) 500 mg/dL regardless of ketone level
  - For subjects 2-6 year olds, SMBG will be used. All applicable rules related to rescue therapy/low glucose guidelines, will be based on SMBG rather than YSI™\*.
- Ketone greater than or equal ( $\geq$ ) to 3 mmol/L regardless of blood glucose
- Persistent ketone level greater than or equal to ( $\geq$ ) 1.5 mmol/L after hydration (see ketone management guidelines Section 10.5.4)
- Subject develops nausea, vomiting or abdominal pain
- Maximum blood volume drawn:
  - 4 mL/kg (inclusive of all YSI™\* FST days) during this study or 400 cc whichever is more for subjects' age 14-80 years old. However, no more than 2 mL/kg of blood volume in a 24-hour period is to be drawn.
  - 3 mL/kg (inclusive of all YSI™\* FST days) during this study for subjects' age 7-13 years old.
  - 50 mL will be maximum blood volume for subjects' age 2-6 years old. However, no more than 1 mL/kg of blood volume in a 24-hour period is to be drawn.

## 10.10.2. Stopping Rules for Entire Study

During the study, the following steps will be taken for:

- DKA during Hypoglycemic and Hyperglycemic Challenges
- Severe hypoglycemia with seizures or requiring glucagon during Challenges

1. Site will notify the sponsor within approximately 24 hours of receiving knowledge of the event.
2. Sponsor will notify Food and Drug Administration (FDA) within approximately 72 hours of knowledge of the event.
3. CEC is to review the event within 7 days from the time that the sponsor is notified.
4. CEC will act as DMC in this situation and will provide recommendation to the sponsor on the following:
  - a) If enrollment and study may continue
  - b) If enrollment should be stopped; enrolled subjects are still allowed to continue in study
  - c) If the entire study must be stopped, including subjects who have already received study devices.

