**Rescue Therapy:**

Rescue therapy outlined in the protocol for hyperglycemia and hypoglycemia are required to be available during the entire hotel/camp stay as defined in the protocol.

- Treatment with Glucagon and ampules of glucose for hypoglycemia are required to be available during the hotel/camp stay
- Treatment with Saline, and IV regular insulin for hyperglycemia are required to be available during the hotel/camp stay.
- Intravenous access is required during challenges for the hotel/camp study as it is for the in-clinic setting during Challenge procedures.

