# CIP324 Clinical Investigation Plan

10838519DOC

Version H

Page 127 of 173

Medtronic

	

Transfer to ER or follow DKA guidelines of the local institution for the disposition of subject if subject is exhibiting signs and symptoms of DKA

Risks with hypoglycemic challenges	Prevention and Mitigation
Risks for hypoglycemia may include: 

Seizure

Coma

Altered mental status

Loss of consciousness

Cardiovascular event

Death

Risk of rebound hyperglycemia with ketosis

	
Prevention and Mitigation include:
 

Follow frequent blood sampling per protocol (See Section 10.5.1)

Clear guidelines for management during hypoglycemic challenge

IV access to give immediate dextrose or other emergency drugs

Qualified investigator presence during experiment.

Limiting the time the subject is allowed to stay in the hypoglycemic ranges

The subject is under constant observation and monitoring at all times during the challenges

Preventing subjects who do not have a carb/insulin ratio from participating in the challenge (observational only)

Investigational centers are to use glucose meter in the event a YSI blood glucose value is not available at the required time interval.

 
Treatment of these risks include:
 

Rescue therapy treatment instructions are provided in the Hypoglycemic and Hyperglycemic Challenge Guidelines

IV administration of dextrose if uncooperative orally with food or liquid

Glucagon if subject does not respond to Dextrose

Immediate withdrawal from study if severe hypoglycemia (stop the challenge, stop the FST and DO NOT continue with any future scheduled frequent sampling days)

 
Transfer to ER or follow severe hypoglycemia guidelines of the local institution for the disposition of subject.

---

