## 12.1. Definitions and Classification of Adverse Events

Medtronic uses the definitions provided in ISO 14155:2011 and 21 CFR 812 for AE definitions. Where the definition indicates "device", it refers to any device used in the study. This might be the device under investigation, or any market released component of the system. Medtronic follows MEDDEV 2.7/3 revision 3 guidelines for classifying causality levels; but will apply these causality definitions across all events, not only serious adverse events and definitions have been adapted accordingly.

1. **Severe Hypoglycemia** is an event requiring assistance of another person due to altered consciousness to actively administer carbohydrate, glucagon, or other resuscitative actions. This means that the subject was impaired cognitively to the point that he/she was unable to treat his or her self, was unable to verbalize his or her needs, and was incoherent, disoriented and/or combative.

These episodes may be associated with sufficient neuroglycopenia to induce seizure or coma. Plasma glucose measurements may not be available during such an event, but neurological recovery attributable to the restoration of plasma glucose to normal is considered sufficient evidence that the event was induced by a low plasma glucose concentration. (**Adapted from American Diabetes Association Workgroup on Hypoglycemia, Diabetes Care 28:1245-1249, 2005**)

2. **Severe Hyperglycemia** is defined as hyperglycemia (blood glucose greater than ( $>$ )300 mg/dL) (16.7 mmol/L) with blood glucose ketones greater than ( $>$ )1.5 mmol/L, urine ketones moderate or large, or accompanied by symptoms of nausea, vomiting or abdominal pain.
3. **Diabetic Ketoacidosis/DKA** diagnostic criteria: blood glucose greater than ( $>$ ) 250 mg/dL (or greater than ( $>$ ) 13.9 mmol/L), arterial pH less than ( $<$ ) 7.3, bicarbonate less than ( $<$ )15mEq/L, moderate ketonuria or ketonemia and requiring treatment within a health care facility. (**American Diabetes Association-Diabetes Care, Volume 27, Supplement 1, January 2004; S94-S102**)

Hyperglycemic events will be recorded as DKA if the event includes the presence of all of the following:

- Arterial blood pH less than ( $<$ ) 7.30 or serum bicarbonate less than ( $<$ ) 15mEq/L
- Blood glucose greater than ( $>$ ) 250 mg/dL (or greater than ( $>$ ) 13.9 mmol/L)
- Serum ketones or large/moderate urine ketones
- Symptoms such as polyuria, polydipsia, nausea, or vomiting

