## 13. Data Review Committees

### 13.1. Clinical Events Committee

A clinical events committee (CEC) consisting of external physicians with an expertise in endocrinology and the management of diabetes including insulin pumps and CGM will be convened. The CEC will review all AEs as required per protocol, and may include reports of:

- Serious Adverse Event
- Serious Adverse Device Effect
- Unanticipated Adverse Device Effect
- Severe Hypoglycemia
- Diabetic Ketoacidosis
- Severe Hyperglycemia

The CEC will review the following events within 7 days from the time the sponsor is notified.

- DKA during Hypoglycemic and Hyperglycemic Challenges
- Severe hypoglycemia with seizures or requiring glucagon during Challenges

CEC will act as DMC in this situation and will provide recommendation to the sponsor on the following:

- a) If enrollment and study may continue
- b) If enrollment should be stopped; enrolled subjects are still allowed to continue in study
- c) If the entire study must be stopped, including subjects who have already received study devices.

The CEC will assess events to determine agreement or disagreement with the investigator classification of an event. The CEC will only provide three causality assessments for device and procedure relatedness: Not Related, Possible, and Causal relationship.

Causality Categories for Investigational Center		Causality Categories for CEC:

• Not Related

• Unlikely

• Possible

• Probable

• Causal relationship

		

• Not Related

• Possible

• Causal relationship

The sponsor will notify the investigator of any disagreement in assessment of an event by the CEC.

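### The study-level hypoglycemia trigger omits loss of consciousness, so an unconscious subject who recovers on IV dextrose does not automatically start the FDA notice or the 7-day CEC review

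*Protocol*

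**What the plan says.** The trigger has two event types: DKA during challenges, and "Severe hypoglycemia with seizures or requiring glucagon during Challenges". It is worded identically in the Synopsis, Section 10.10.2 and Section 13.1. All three attach the 7-day CEC review and the CEC-as-DMC recommendation to it. The Synopsis and Section 10.10.2 also attach the FDA notice.

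The definition of severe hypoglycemia in Section 12.1 is wider. It needs altered consciousness and another person's help, but neither seizure nor glucagon. It adds: "These episodes may be associated with sufficient neuroglycopenia to induce seizure or coma".

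For rescue during hypoglycemic challenges, the Section 11.1 risk table lists "IV administration of dextrose if uncooperative orally with food or liquid" and then "Glucagon if subject does not respond to Dextrose". Section 5 makes IV access a condition of challenges: "Intravenous access is required during challenges for the hotel/camp study as it is for the in-clinic setting during Challenge procedures". Section 11.1 leaves the detail to another document: "Rescue therapy treatment instructions are provided in the Hypoglycemic and Hyperglycemic Challenge Guidelines".

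The subject-level rule in Section 10.9 is broader than the study-level one: "Subject will be withdrawn from the study if subject experiences diabetic ketoacidosis, unconsciousness or severe hypoglycemia".

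**The concern.** The study-level trigger depends on a seizure or on which rescue drug was needed. With a working IV line, the expected first rescue is dextrose, and dextrose is not in the trigger. Loss of consciousness caused by a study procedure could therefore be reversed without any step under Section 10.10.2 starting.

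Section 11.4 rates the study as significant risk because of the challenges. Sections 10.10.2 and 13.1 give the CEC its DMC role only for the listed events. For this subject the protocol thus sets no deadline for committee review and requires no recommendation on whether the study should go on.

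Elsewhere the protocol treats loss of consciousness much like seizure. Each is a separate 6-month exclusion (Section 7.4, criteria 7 and 8). Both stand in one rescue-and-withdrawal bullet for observation-only subjects (Section 10.5.5). Both are listed risks of the hypoglycemic challenge (Section 11.1). The study-level trigger keeps one and leaves out the other.

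**Working it through.** This is mainly a check of wording. Take a subject in a hypoglycemic challenge who loses consciousness, does not seize, recovers on IV dextrose and gets no glucagon.

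| Rule | Section | Applies? |
|---|---|---|
| Severe hypoglycemia definition | 12.1 | Yes |
| Withdrawal of the subject | 10.9, 10.10.1 | Yes |
| Report to the sponsor, desired within 24 hours | 12.3 | Yes |
| Reported as an adverse event during sampling | 12.8 | Yes |
| SAE (life-threatening, or intervention to prevent life-threatening injury or permanent impairment) | 12.1 | Probably |
| Routine CEC review | 13.1 | Possible; no deadline given |
| Seizure arm of the study-level trigger | 10.10.2 | No |
| Glucagon arm of the study-level trigger | 10.10.2 | No |
| FDA notice, 7-day CEC review, CEC-as-DMC recommendation | 10.10.2, 13.1 | Not started |

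The result is the same whether the glucagon condition is read as qualifying severe hypoglycemia or as standing alone.

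Could another route supply the missing steps?

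- Routine CEC review is optional in its wording: "The CEC will review all AEs as required per protocol, and may include reports of", followed by a list that includes severe hypoglycemia and SAEs. No time limit or DMC role is attached to it.
- Reporting as an unanticipated adverse device effect (Section 12.4) would not be expected to apply, because loss of consciousness is already a listed risk of the challenge.
- SAE reports to the sponsor and, when required, the IRB (Section 16.2), and the suspension powers in Sections 17.9 and 17.9.1, carry no committee deadline.

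The rescue route can decide the outcome. The protocol foresees IV occlusion (Sections 10.3 and 10.5.2). If an occluded line led to glucagon being given instead, the same unconscious subject would start the study-level steps.

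For scale, count targeted hypoglycemic challenges among planned completers, at 2 per challenged subject, assuming exactly 20 of those aged 14-80 are observation-only (the stated minimum, Section 7.6):

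- Ages 14-17: minimum 24; maximum 122 - (15 + 15 + 20 + 20) = 52.
- Lower count: (122 + 24 - 20) × 2 = 252.
- Upper count: (122 + 52 - 20) × 2 = 308.

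This does not bound exposure. Up to 460 - 244 = 216 further enrolled subjects are left out, some of whom would have no challenges. More observation-only subjects, or stopping at N = 100 (Section 15.15), would lower the count.

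**The case against.** The best defence is that the narrow trigger is a coherent second tier. Any severe hypoglycemia or unconsciousness ends the subject's participation; study-level review is kept for seizure or, given the rescue order, for failure of first-line treatment. The wording is consistent in three places, and the version history shows that the stopping rules were revised in versions B and F. A reader might infer an internal contradiction. The documents do not support that, and the narrower tier may be intended, although no reason is given for leaving out loss of consciousness.

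A reader might also infer that such an event would go unseen. It would not: the sponsor learns of it on about the same timescale as for a triggering event, and can act under Sections 17.6 and 17.9. Only the automatic review and its deadline are missing.

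It is also tempting to make any need for IV dextrose a trigger. Section 11.1 gives dextrose to anyone who will not cooperate orally, and Section 12.1 already counts disoriented or combative subjects as severe. Such a trigger would bring in conscious but confused subjects and largely merge the two tiers.

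Finally, the dextrose-first order for challenges rests on two risk-table bullets. The fuller text in Section 10.5.5 is headed for observation-only subjects, and the Challenge Guidelines were not available. They may add escalation. This limits confidence but does not change what Section 10.10.2 says.

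**Conclusion.** The point holds as an optional improvement, with medium confidence. Loss of consciousness without seizure that is reversed by IV dextrose lies outside the study-level trigger, and no other section of the protocol sets the FDA notice, the 7-day clock or the DMC recommendation for it.

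Its size cannot be estimated, because the documents give no event rate; the challenge count is not a forecast of events. Constant observation and limited time in the hypoglycemic range (Section 11.1), 5-minute sampling below 75 mg/dL (Section 10.5.1) and the 6-month exclusions all lower the likelihood. The conclusion assumes the rescue order in Section 11.1 is followed and that the Challenge Guidelines add no equivalent escalation.

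**What to change.** First check the Challenge Guidelines for the rescue order and any escalation. Then reword the bullet in the Synopsis, Section 10.10.2 and Section 13.1 to: *Severe hypoglycemia with seizure or loss of consciousness, or requiring glucagon, during Challenges*. Do not add IV dextrose, so that a conscious but confused subject who receives it stays in the subject-level tier.

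The cost is one bullet in three places, made by amendment under Section 17.6: IRB approval, investigator signatures at up to 17 centers, and regulatory submission if applicable. Any CEC document that repeats the bullet changes too. Each added event then brings one FDA notice and one 7-day CEC review. How many there would be is unknown, but sites already report these events to the sponsor.

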**• Diabetes cohort based on exercise activity:**

- 18 – 80 years
  - N=minimum of 22 subjects
- 14 - 17 years
  - N= minimum of 6 subjects
- 2 - 13 years
  - N= minimum of 20 subjects
- Sponsor may instruct site for exercise to be performed in order to obtain low glucose values

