## Hypoglycemic and Hyperglycemic Challenges

### **Subjects 2 - 13 years:**

During the day of YSI™\*/SMBG FST, subjects (2 - 13 years) will not participate in hypoglycemic and hyperglycemic challenges.

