**Figure 5. Visit Schedule Subjects 2-6 Years**

## 9.2.2.2. Visit 1: Consent and Screening

### Overview General

#### Investigational center staff will:

- Obtain California Experimental Subject's Bill of Rights (if applicable), Informed Consent Form (ICF) /Assent form, and HIPAA form from the subjects
- Assess subject eligibility to participate in the study
- Obtain demographic and baseline characteristics including:
  - Age
  - Gender
  - Race
  - Ethnicity
  - Prior medical history
  - Height and Weight
    - Note: BMI will be calculated automatically in the study database, based on height and weight measurements entered.
  - Concomitant medications (Screening Only)
  - Date of diabetes diagnosis
  - Insulin carbohydrate ratio and insulin sensitivity for subject's insulin requiring, if applicable
- Complete required screening tests, if all eligibility criteria are met:
  - Perform urine test for pregnancy, female subjects of child bearing age or capability
  - Obtain blood sample:
    - Hct
      - Send to Central Laboratory, or clinic's own lab for required screening tests. There is no point of care (POC) testing for Hct.
      - If patient has prior Hct from routine care done within 6 months of enrollment and the report of lab placed with subject source documents, then no blood needs to be done.
      - HbA1c (not an eligibility criteria)
    - Send to Central Laboratory
    - Note: For all out of range lab results, a single re-test is permitted
  - Per Investigator's discretion, subjects may participate in the exercise cohort. Exercise cohort subjects will be asked to exercise for a minimum of 60 minutes during SMBG FSTs.

- Enter electronic Case Report Forms (eCRF)s into the study database as appropriate
- Schedule next visit date and time

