### **Exercise:**

Subjects are required to begin exercise at start of YSI™\*/SMBG FST if their glucose is between 100-300 mg/dL mg/dL. They should continue exercise for at least 60 minutes. This exercise can be in the form of playing or moving around. We recommend the sites provide toys and games for young subjects to use during the exercise period. However, exercise should be stopped, and meal administered and/or glucose given when:

- Glucose is less than or equal to 70 mg/dL for subjects 2-6 years of age
- Glucose is less than or equal to 65 mg/dL for subjects 7-13 years of age

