# CIP324 Clinical Investigation Plan

10838519DOC

Version H

Page 128 of 173

Medtronic

Risks with exercise:	Prevention and Mitigation

Risks for exercise may include:
 

• Hyperglycemia: DKA, symptomatic ketosis, cardiovascular event and dehydration.

• Hypoglycemia: seizure, coma, altered mental status, loss of consciousness, cardiovascular event and death and risk of rebound hyperglycemia with ketosis.

• Musculoskeletal injury: sprain and bone fracture.

• Cardiovascular event

	
Prevention and Mitigation include:
 

• Follow frequent blood sampling per protocol (See Section 10.5.1)

• Clear guidelines for management during both hypoglycemic and hyperglycemic challenge

• IV access to give immediate insulin or dextrose

• Qualified Investigator presence during experiment

• Stopping challenge procedures if ketones are elevated or if subject is exhibiting signs and symptoms of DKA (Please refer to the ketone management guidelines in the protocol)

• Limiting the time the subject is allowed to stay in the hypoglycemic and hyperglycemic ranges

• The subject is under constant observation and monitoring at all times during the challenges

• Preventing subjects who do not have a carb/insulin ratio from participating in the challenge (observational only)

• Investigational centers are to use glucose meter in the event a YSI blood glucose value is not available at the required time interval.

 
Treatment of these risks include:
 

• IV insulin for hyperglycemia if needed

• IV dextrose for severe hypoglycemia

• Rescue therapy treatment instructions are provided in the protocol or hypoglycemia and hyperglycemia

• Immediate withdrawal from study if subject is exhibiting signs and symptoms of DKA or severe hypoglycemia (stop the challenge, stop the FST and DO NOT continue with any future scheduled frequent sampling days)

• If there is a suspected sprain or bone fracture, the subject will be sent to the Urgent care or ER.

• Calling 911 and then transfer to ER

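### The study-level safety steps start only for events during challenges, so no event in an FST at ages 2-13, or in an observation FST at 14-80, can start them.

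*Protocol*

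**What the plan says.** Protocol section 10.10.2 names two trigger events: DKA during the hypoglycemic and hyperglycemic challenges, and "Severe hypoglycemia with seizures or requiring glucagon during Challenges". Four steps follow:

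- The site notifies the sponsor within about 24 hours.
- The sponsor notifies FDA within about 72 hours.
- The CEC reviews the event within 7 days.
- The CEC, acting as DMC, recommends continuing, stopping enrollment, or stopping the whole study.

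The synopsis repeats this. Section 13.1 says "The CEC will review the following events within 7 days from the time the sponsor is notified" and lists the same two challenge-bound events. For serious and severe glycemic events in general, section 13.1 is looser: "The CEC will review all AEs as required per protocol, and may include reports of" a list that includes severe hypoglycemia and DKA, with no deadline and no stated stop-or-continue recommendation.

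Section 9.1 states that "subjects (2 - 13 years) will not participate in hypoglycemic and hyperglycemic challenges". On exercise at these ages, section 9.2.2.6.2 says "Subjects are required to begin exercise at start of" the FST when glucose is 100-300 mg/dL and asks for at least 60 minutes. Exercise stops, and a meal and/or glucose is given, at 70 mg/dL or below (2-6 years) or 65 mg/dL or below (7-13 years). Section 7.1 adds, under the exercise cohort, that the sponsor may instruct exercise to obtain low glucose values.

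**The concern.** The rule depends on the procedure under way, not on the event. A seizure during an adult's challenge brings the 72-hour FDA notice, the 7-day CEC review and the CEC recommendation. The same seizure in a 4-year-old's FST brings none of them. Leaving children out of challenges lowers their exposure to induced glucose extremes, but it does not empty their sessions of risk. They exercise during the FST, and section 11.1 lists as an exercise risk "Hypoglycemia: seizure, coma, altered mental status, loss of consciousness, cardiovascular event and death and risk of rebound hyperglycemia with ketosis".

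There is also an inconsistency across ages. In section 8.2.2.6.3 the exercise cohort aged 14-80 is expected to exercise during the hyperglycemic challenge, so a trigger event there falls inside the rule. A trigger event during exercise at ages 2-13 falls outside it.

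At stake is whether someone outside the sponsor must decide promptly, after such an event, if the study should go on.

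**Working it through.** The point rests on text, and the plan gives no figure of its own to reproduce. The arithmetic only sizes the part of the study outside the rule.

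**Step 1: can any event at ages 2-13 start the steps?** Both triggers in section 10.10.2 require the event to occur during a challenge, and section 9.1 excludes ages 2-13 from challenges. So none can. The timing tables for ages 2-6 and 7-13 have a column heading that mentions the start of a challenge, but only if applicable, and section 9.1 settles that it is not. The same logic leaves out observation FSTs at ages 14-80 (sections 7.6 and 8.2.2.6.3).

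**Step 2: subjects.** Inputs are the age-group minimums and the target of 244 completers (section 5).
- Lower figure, sum of minimums for ages 2-13: 15 + 15 + 20 + 20 = 70; 70/244 = 28.7%.
- Upper figure, if ages 14-17 stay at their minimum of 24: 122 − 24 = 98; 98/244 = 40.2%.

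**Step 3: sessions.** Section 15.7 gives 4 FSTs per subject at ages 14-80 and 2 at ages 2-13.
- With 70 children aged 2-13, ages 14-17 number 122 − 70 = 52. Ages 2-13: 70 × 2 = 140. Total: 122 × 4 + 52 × 4 + 140 = 836. Share: 140/836 = 16.7%.
- With 98 children aged 2-13: 98 × 2 = 196. Total: 122 × 4 + 24 × 4 + 196 = 780. Share: 196/780 = 25.1%.

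**Step 4: observation at ages 14-80.** Section 7.6 sets a minimum of 20 subjects under observation. If all four of their FSTs are observation (an assumption; the text does not say so), this adds 20 × 4 = 80 sessions. The total outside the rule is then 140 + 80 = 220 of 836 (26.3%) or 196 + 80 = 276 of 780 (35.4%).

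**Step 5: how much exercise?** The protocol is not consistent. Section 9.2.2.6.2 makes exercise a requirement within the glucose range. Section 9.2.2.2 says "Per Investigator's discretion, subjects may participate in the exercise cohort", and section 7.1 asks for "N= minimum of 20 subjects" at ages 2-13. Exercise sessions therefore run from 20 × 2 = 40, if only the minimum cohort exercises, up to the full 140 to 196, if every child starts in range. The gap does not depend on which is right, because every FST at these ages is outside the rule.

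**Step 6: what still applies to such an event?**
- Withdrawal and individual stopping (sections 10.9, 10.10.1): all ages, but they act on that subject only.
- Site report to the sponsor, desired within 24 hours (section 12.3): applies to severe hypoglycemia and DKA.
- General CEC review (section 13.1): possible, with no stated deadline or continue-or-stop mandate.
- Suspension or termination by the sponsor or a regulator (section 17.9): applies to the whole study, but is discretionary and names no trigger event.
- FDA notice in about 72 hours, CEC review in 7 days, CEC acting as DMC (section 10.10.2): do not apply.

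**The case against.** The best defense is that the rule follows the stated hazard. Section 11.4 says the devices pose no significant risk and rests the significant-risk rating on the challenges. Reserving an expedited rule for deliberately induced glucose extremes is a coherent choice. This may well explain the scope. It does not justify leaving out the identical event in another FST, given required exercise and the sponsor's option to instruct exercise to reach low values.

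A second defense is that study-level authority already exists. Section 17.9 lets the sponsor or a regulator stop the study if risk proves higher than first indicated, and section 17.9.1 obliges investigators to assess stopping at their own center when risks are found to outweigh benefits. This stands, and it limits the point. A reader might infer that these children have no safety oversight, or that nobody could stop the study on their account. The documents do not support that. Only the trigger, the deadlines and the CEC's mandate are absent. No CEC charter is among the documents, so this is shown for the protocol alone.

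A third defense concerns exercise. Section 11.1 lists matching hypoglycemia harms for exercise and for the hypoglycemic challenge, and a reader might infer that the two carry equal risk. They cannot be equated on that basis: a list of possible harms says nothing about frequency. Exercise also has the 70 and 65 mg/dL stops, and sampling tightens to every 5 minutes below 75 mg/dL (7-80 years) or 70 mg/dL (2-6 years) under section 10.5.1. This objection stands in full, and the session shares above measure coverage, not risk.

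**Conclusion.** The concern holds as a gap in the study-level rule. No event in an FST at ages 2-13 can start the section 10.10.2 steps, and nor can one in an observation FST at ages 14-80. Ages 2-13 account for 70 to 98 of 244 completers (29% to 40%) and 140 to 196 planned sessions (17% to 25%). The upper figures assume ages 14-17 finish at their minimum of 24. All figures use planned completers and scheduled FSTs, without repeats or an early stop at an interim analysis.

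The documents give no event rate, so how often the gap would matter cannot be computed. The change is worth making because it is narrow and cheap and covers the youngest subjects. The plan is not unsafe without it.

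**What to change.** In section 10.10.2, the synopsis and section 13.1, remove the restriction to challenges from both trigger events and put in its place: *during any YSI/SMBG FST (challenge, observation or exercise), at any age*. Leave the event definitions, the 24-hour, 72-hour and 7-day steps and the three CEC options as they are.

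The cost is a protocol amendment, with regulatory approval if applicable, IRB approval and investigator signatures (section 17.6). There may be a few more expedited CEC reviews and FDA notices; the number cannot be computed without an event rate. The CEC could recommend stopping enrollment or the study after such an event, which is the purpose of the change, but the rule itself brings no automatic pause. No extra subjects, visits or blood draws are needed.
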